Protocol

1. Project/Grant Title: Adaptability and Resilience in Aging Adults (ARIAA)-2B

2. Investigators: [name]. (PI)

3. Trial Registration: NCT04068922

4. Abstract: Growing evidence supports the presence of dysregulated pain modulation in older adults, an effect which may heighten age-associated risk for chronic pain. While persistent pain is common in older adults, chronic low back pain is the leading cause of disability in this population and results in significant impairment in psychosocial and physical functioning. Given reports of suboptimal treatment of pain in older adults, improvements in pain management in this cohort are of critical importance. Resilience is characterized as a dynamic process resulting in positive adjustment and adaptation after exposure to adversity. The benefits of resilience in health-related functioning are manifold, and evidence suggests that resilience plays an important role in fostering adaptive physiological and affective responses to pain. Given this, capitalizing on positive resources is a promising target for enhancing pain adaptation, and is especially salient to older adults given the burden of high-impact pain in this group. Therefore, the aim of this project will be to conduct a Stage I pilot study and examine the feasibility and acceptability of a resilience intervention for chronic low back pain among older adults. Using a Science of Behavior Change approach, the proposed study will examine intervention-related benefits in psychosocial and physical functioning, and assess whether changes in targeted resilience mechanisms result in improvement in pain-associated outcomes. Achievement of these aims will provide a rich platform for future intervention research and will forge a path toward investigating psychological therapies of resilience that improve pain and disability among geriatric populations.

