Using a Stage Model approach (20), the primary aim of this study is to examine the feasibility and acceptability of a resilience intervention for chronic pain among older adults. Intervention modules will specifically engage hope, self-efficacy, positive affect, and pain acceptance as these factors demonstrated the strongest relationships with clinical pain, disability, and psychological functioning from the PI's previous work (NIH K99 Award). Chronic low back pain (cLBP) will be the targeted population given that it represents the most debilitating and therapeutically-challenging pain condition among geriatric populations. We will conduct a pilot study to test the feasibility and acceptability of the intervention in this patient population (primary aim), explore whether the intervention engages the proposed resilience targets (i.e., hope, self-efficacy, positive affect, pain acceptance), and assess whether changes in these factors result in improvements in pain outcomes (i.e., NIH Science of Behavior Change approach (21)). Achievement of these aims will provide a strong framework for future intervention research examining mechanisms that promote adaptive health and pain-related functioning in aging populations.

Specific Aim 1: *Conduct a pilot test to examine feasibility, acceptability, and tolerability of a resilience intervention for older adults with cLBP.* We will assess adherence and retention rates, and evaluate ratings of acceptability through brief assessments and eliciting qualitative feedback from participants at post-intervention. **Hypothesis 1.** Individuals in the resilience intervention will report high adherence to and satisfaction with the intervention.

Specific Aim 2: *Assess whether a resilience intervention facilitates improvements in hope, self-efficacy, positive affect, and pain acceptance and whether changes in these processes result in improved pain-related outcomes.* Intervention modules will be adapted from the existing positive psychology literature and validated self-report measures will be used to verify engagement in the specific resilience targets. **Hypothesis 2.** We hypothesize that a resilience intervention will improve pain severity, pain interference, negative affect, and quality of life by increasing hope, self-efficacy, positive affect, and pain acceptance.

7. Research Plan:

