Participants. We will recruit adults, ages 50+ years, from the community and physician referral. To permit sex-stratified exploratory analyses, an equal number of men and women will be targeted (23). Participants must endorse pain in the lower back region (i.e., space between the lower posterior margin of the rib cage and the horizontal gluteal fold) (24), and report pain of a moderate intensity (rating of ≥ 3 on a numeric rating scale ranging from 0-10) occurring on at least half of the days in the past 6 months. Pain must moderately interfere with their daily activities (rating of ≥ 3 on a numeric rating scale ranging from 0-10). In order to generalize results more broadly, study entry will not be restricted to low back pain although participants must identify low back pain as their primary pain condition. Exclusion criteria are as follows: 1) current participation in another psychological treatment; 2) severe psychiatric illness not adequately controlled by medication (e.g., schizophrenia, bipolar disorder) or other conditions anticipated to impair intervention engagement (e.g., substance abuse/dependence); 3) presence of chronic, malignant pain (e.g., HIV, cancer) or systemic inflammatory disease (e.g., rheumatoid arthritis, ankylosing spondylitis, systemic lupus erythematosus, etc.); 4) significant cognitive impairment on the Montreal Cognitive Assessment (25); 5) inability to read and write English; and 6) if currently taking prescription analgesic or psychotropic medication, must be stabilized on these treatments for ≥ 4 weeks prior to the baseline assessment. Participants are also encouraged to refrain from starting any new treatments for pain while participating in the study. These include, but are not limited to, seeing a new chiropractor, physical therapist, massage therapist, psychiatrist, or counselor, taking new opioid medications for pain or receiving epidural or cortisone injections, or using medical marijuana or CBD oil. If a participant begins a new pain treatment during study participation, the study PI will evaluate and decide whether or not it is cause for exclusion. All participants will be required to wear Personal Protective Equipment (PPE) during in-person visits. PPE (masks) will be provided by study staff upon participant arrival or participants may bring their own. If intervention sessions are conducted through PHI Zoom, study staff will ensure participants have access to Zoom as well as a stable internet connection. During Zoom intervention sessions, participants must have access to a working camera and microphone and have them both turned on in order to participate. Study staff will also ask participants if they have access to a space that will provide confidentiality (e.g. not conducting Zoom call where other people may overhear, inform other household members about confidentiality expectations, ensure no identifying information is visible through camera). Zoom tutorials will be provided during the Baseline Session.

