
3-Month Follow-Up Assessment

Questionnaires will be administered via REDCap approximately 12 weeks after completion of the intervention to be completed online at home. These questionnaires will assess pain intensity and interference, mood, quality of life, and use of intervention materials and skills since the conclusion of the group sessions.

Study Questionnaires:

Several questionnaires will be administered to assess general health, pain-related symptoms, and psychological functioning. In order to distribute participant burden, some of the questionnaires administered during Visit 1 and Visit 8 will be dispensed either during the session or at home between sessions (either via our secure internet-based data collection system [i.e., REDCap] or on paper, depending on the participant's preference).

Measures of Treatment Acceptability. Treatment credibility questions (38) were adapted for the current study as a treatment expectancy measure and will be administered during Visit 1 and Visit 2 consisting of the following items: 1) reasonableness of treatment, 2) willingness to undergo treatment, 3) confidence in recommending the treatment to others, 4) confidence that the treatment will help with pain coping, 5)

IRB Project #: 201901927

IRB Version: 12/16/2021

confidence that the treatment will decrease pain, 6) confidence that the treatment will eliminate pain, and 7) expectation for improvement.

The 8-item Client Satisfaction Questionnaire (CSQ-8) (39) will be administered after the intervention as an assessment of treatment satisfaction. Items are rated on a 4-point Likert scale and measure aspects related to the quality of treatment, willingness to recommend the treatment, and general satisfaction with the treatment.

As a treatment evaluation and to better understand their perceptions of the intervention, participants will be queried at posttreatment on their satisfaction with the intervention components, contentment with the structure of the intervention, and recommendations for intervention improvement. Participants will also be asked to indicate the usefulness of each intervention session module and home activity on a 5-point Likert scale ranging from 0 ("not at all") to 4 ("extremely").

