Statistical Methods. The goal of the study will be to target 50 participants for the pilot intervention. Accounting for a conservative 20% attrition rate, we will recruit an additional 10 participants (Total $N=60$). This sample size is feasible and will provide stable estimates of dropout rates, feasibility, and acceptability of the intervention protocol. We anticipate screening an additional 70 participants who may not meet eligibility criteria (i.e., screen failures). **Data Analysis: Specific Aim 1.** The analysis of feasibility, tolerability, and acceptability outcomes will be predominantly conducted with descriptive statistics, with means and standard deviations reported. To assess feasibility, we will calculate a ratio between participants enrolled versus the number of participants commencing treatment. Tolerability will be examined by measuring completion rates (i.e., participants completing all seven sessions of the intervention). Participant acceptability of the intervention will be assessed through treatment credibility ratings and satisfaction with the program (59). Chi-square tests and between-group t -tests will be used to compare group differences in baseline characteristics between completers and participant dropouts. **Specific Aim 2.** To assess change in primary study outcomes (i.e., pain severity, pain interference, negative affect, quality of life), mean differences from pre- to post-intervention will be calculated using paired samples t -tests. Clinical significance of treatment changes will be determined by identifying participants whose raw change score for each outcome variable is greater than one-half of a standard deviation from their baseline score (60, 61). Using residualized change scores (i.e., difference between the post-intervention value with the pre-intervention score covaried out), Pearson correlations will be computed to examine associations between outcome and treatment target change scores.

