for chronic low back pain. Participants who complete the resilience intervention are expected to show improvement in pain severity, interference, negative affect, and quality of life. Overall, it is believed that the data will provide important insight into the effects of resilience-based interventions on clinical pain and functioning. Ultimately, such knowledge may enhance quality of life and reduce pain in the targeted population, as well as lead to advances in the treatment of pain in older adults.

Importance of the Knowledge to Be Gained. Chronic low back pain results in significant impairment in older adults, as well as tremendous individual and societal burden. The data obtained from the current study has the potential to advance treatment strategies for the management of chronic low back pain in older adults and may have broader implications for other medical populations likely to suffer from chronic pain. Moreover, our findings will enhance the understanding of underlying mechanisms contributing to treatment-related effects in our proposed pain and psychological outcomes.

Inclusion of Women and Minorities. Both male and female subjects will be recruited with the goal of equal gender distribution. It is planned that adult minorities (50+ years) will be included in the study sample in proportion to census levels in the Gainesville, Florida community including: 20% African-American, 6% Asian, 5% Hispanic or Latino, and 3.6% More than One Race. To ensure that the study sample includes census levels of minorities, we will assess their representation periodically over the course of the study and adjust recruitment or over-sample as needed.

10. Conflict of Interest: There is no conflict of interest involved with this study beyond the professional benefit from academic publication or presentation of the results.

References:

2. The U. S. Burden of Disease Collaborators. The state of US health, 1990-2016: Burden of diseases, injuries, and risk factors among US states. *JAMA*. 2018;319(14):1444-72.

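### Aim 2 reads an uncontrolled pre-to-post change in a single arm as the benefit of the intervention, so Hypothesis 2 can be supported when the intervention does nothing

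*Combined protocol and SAP*

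**What the plan says.** The study has one group, and everyone who starts receives the seven-week programme. For Aim 2, section 7 (Statistical Methods) states that "mean differences from pre- to post-intervention will be calculated using paired samples" t-tests, for pain severity and interference, negative affect and quality of life. The only between-group tests compare completers with dropouts. The same section adds a responder rule: "Clinical significance of treatment changes will be determined by identifying participants whose raw change score" exceeds half a standard deviation.

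The change is read causally in several places:
- Section 4 (Abstract): "the proposed study will examine intervention-related benefits in psychosocial and physical functioning".
- Section 6, Hypothesis 2: "We hypothesize that a resilience intervention will improve pain severity, pain interference, negative affect, and quality of life".
- Section 7 (Statistical Methods): the responder rule speaks of treatment changes.
- Section 9 (Possible Benefits): "the data will provide important insight into the effects of resilience-based interventions on clinical pain and functioning".

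Section 7 (Participants) sets two entry cut-offs. People must "report pain of a moderate intensity (rating of ≥ 3 on a numeric rating scale ranging from 0-10"), and "Pain must moderately interfere with their daily activities (rating of ≥ 3 on a numeric rating scale ranging from 0-10").

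Outcome questionnaires are placed at Visit 1, Visit 8 and three months. Visit 2 has a form already, because the credibility items serve "as a treatment expectancy measure and will be administered during Visit 1 and Visit 2", but no outcome measure is assigned to it. Under Confidentiality, staff are told not to record phone-screen answers, so no earlier pain score is kept. Regression to the mean, natural course and the missing comparator are not mentioned.

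**The concern.** A paired t-test in one arm tests whether the mean changed. It does not test why. Four things besides the programme can move the mean in the favourable direction: regression to the mean in people admitted because two ratings were high enough, the natural course of back pain, group contact and attention, and expectancy. The plan has nothing that measures or bounds any of them, and its wording assigns the whole change to the intervention. Hypothesis 2 could therefore be declared supported for a programme with no effect. The proportion passing the half-SD rule would look like a treatment response rate. An inflated estimate could also be carried into later intervention research, for which the abstract and section 6 say this pilot is to be the base.

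**Working it through.** **The plan's own figure.** The target is 50, and 20% attrition is covered by adding 10: 50 × 1.20 = 60, which reproduces the stated N. At 20% attrition, 60 × 0.80 = 48 pairs remain, so n = 48 is used below. The plan states no alpha, sidedness, power or SD for the Aim 2 tests.

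**Assumptions not in the documents.** Two-sided 5% (2.5% in the direction of improvement), normal scores, pre-post correlation r of 0.6–0.8, true effect zero.

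**1. Drift from any source.** In baseline SD units the SD of change is √(2(1−r)): 0.894, 0.775 and 0.632 at r = 0.6, 0.7 and 0.8. The noncentrality is drift/√(2(1−r)) × √48. At drift 0.2 and r = 0.7 this is 0.2/0.775 × 6.93 = 1.79, and the noncentral t with 47 df gives 42%.

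| Drift (SD) | r = 0.6 | r = 0.7 | r = 0.8 |
|---|---|---|---|
| 0.1 | 12% | 14% | 19% |
| 0.2 | 33% | 42% | 57% |
| 0.3 | 62% | 75% | 90% |

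This result does not depend on the entry cut-off.

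**2. The part due to the entry cut-off.** If the score that must pass the cut-off is also the baseline score, the expected fall is (1−r) × φ(c)/p SD, where p is the share passing and c the matching normal cut-off. The plan expects 70 screen failures beside 60 enrolled, so at least 60/130 = 46% pass. That lower limit for p is reached only if every failure is on pain. There, φ(c)/p = 0.397/0.4615 = 0.860, and the fall is 0.4 × 0.860 = 0.34 SD at r = 0.6 and 0.2 × 0.860 = 0.17 SD at r = 0.8. The last column comes from simulating the paired t-test 20,000 times.

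| Share passing the pain cut-off | Regression (SD) | Significant improvement, no effect |
|---|---|---|
| 46% (limit) | 0.17–0.34 | 48–80% |
| 80% | 0.07–0.14 | 12–20% |
| 90% | 0.04–0.08 | 6–9% |
| 95% | 0.02–0.04 | 4–5% |

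If the cut-off is applied only at the earlier screen and errors are independent between occasions, regression between baseline and post is zero.

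**3. The half-SD rule.** With no effect and no drift, the share changing by more than 0.5 SD is 1 − Φ(0.5/√(2(1−r))): 29% at r = 0.6 and 21% at r = 0.8. With the regression in step 2 added (threshold half the SD of the selected group), it is 25–52%.

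**4. What a Visit 2 score would buy.** If error is purely occasion-to-occasion, taking Visit 2 as the pre score removes regression entirely. If flares decay over weeks (assumed weekly autocorrelation 0.85–0.90, 1–4 weeks between Visits 1 and 2) and the cut-off score is the baseline score, regression falls from 0.35–0.40 to 0.08–0.15 SD at 46% passing, and from 0.14–0.16 to 0.03–0.06 SD at 80%. Natural course over the roughly six weeks from Visit 2 to Visit 8 stays in the estimate.

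The Visit 1-to-2 change has a 95% half-width of t × √(2(1−r))/√n: 0.18–0.26 SD with 48 people, or 0.17–0.24 SD with an assumed 55 starters. Subtracting it from the later change needs a gap of similar length, and at r = 0.7 and n = 48 it widens the half-width from 0.22 to 0.39 SD.

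**The case against.** This is a Stage I pilot. Feasibility and acceptability are the primary aim, section 6 says target engagement will be explored, the sample size is justified only for dropout, feasibility and acceptability, and the Data and Safety Monitoring section says this is not a formal clinical trial. Entry also limits short-term fluctuation and co-intervention: pain on at least half the days over six months, prescription analgesics and psychotropics stable for at least four weeks, new pain treatments discouraged. All of this is true and lowers the severity. It does not withdraw the attribution. Hypothesis 2 is stated causally, and the analysis section calls these four measures primary study outcomes.

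The objection on size also stands in part. A reader might infer that the cut-off alone produces a large spurious effect. The documents do not support that. The pain questions come at an initial screen before baseline, the pain outcomes use PROMIS short forms rather than the entry rating, and the protocol does not say whether the ratings are re-applied at baseline. The 46% limit is unlikely, since cognitive impairment, inflammatory disease and concurrent psychological treatment also exclude people. Negative affect and quality of life have no cut-off and are reached only through correlation with pain.

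Finally, no section says that the Aim 2 estimate will be used to size the next trial. The documents promise only a base for later work, so that harm is a risk and not a stated plan.

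**Conclusion.** The point holds. Aim 2 is an uncontrolled within-person comparison, and its result is worded as intervention benefit. Under the assumptions above, modest drift of 0.1–0.3 SD from any source raises the chance of a significant improvement with no effect from 2.5% to roughly 12–90%. The contribution of selection is unknown: near zero if the cut-off is applied only at the earlier screen with independent error, larger if it is re-applied at baseline.

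A reader might also infer that a second score at Visit 2 would separate drift from effect. It would not. Natural course during the treatment weeks, slowly decaying flares, attention and expectancy all remain. The waiting-period change would be known only to about ±0.17–0.26 SD, as wide as most of the regression it is meant to show. The gap between Visits 1 and 2 has no stated length, and some Visit 1 forms may be completed at home afterwards.

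Severity: should fix, because the aim is secondary in a feasibility pilot and the essential correction is to the conclusion drawn.

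**What to change.** 1. **Limit the claim (essential).** In the Abstract, section 6 (Aim 2 and Hypothesis 2), Statistical Methods and section 9, state that Aim 2 estimates within-person change, reported with 95% CIs, that this single-arm pilot cannot attribute to the intervention. State that the proportion changing by more than half an SD is likewise not a treatment response rate, and that the estimate is not to be used alone as the effect size for a later trial. Cost: an amendment to the text, with no new data.

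2. **Add a short repeat at Visit 2 (cheap, optional).** Repeat the pain intensity, pain interference and affect scores before Session 1 begins, and record completion dates for the Visit 1 and Visit 2 forms. Report the Visit 1-to-2 change beside the Visit 2-to-8 change for those outcomes, without subtracting one from the other. State which baseline each analysis uses: quality of life and the correlations with the target measures stay on Visit 1 unless those scales are repeated too. Say plainly that this reduces short-term regression to the mean only. Cost: a few more minutes of questionnaires at a visit that already has a form, and a wait whose length varies between participants.

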Data and Safety Monitoring. Because this is not a formal clinical trial, a data and safety monitoring board (DSMB) will not be required. In order to ensure data integrity and safety of human subjects, adverse events reported by participants to staff members or the PI will be recorded on the "Adverse Event and Unanticipated Problems form" developed by the University of Florida's Institutional Review Board. This form requires a description of the event, the course of action taken, and specification regarding whether or not the event was: 1) serious (e.g., life threatening, requiring or prolonging hospitalization, resulting in significant disability/incapacity or death); 2) unexpected (e.g., consistent with anticipated potential risks outlined in the study protocol/informed consent); or 3) causally related to the study interventions/procedures. All serious and unexpected adverse events are to be reported to the University of Florida IRB (within 5 working days) and the study's sponsor. Other types of adverse events will be monitored and reported to the University of Florida IRB in the study's annual progress review.

The investigators will review the reported adverse events on a weekly basis to minimize the risk to the study subjects.

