Confidentiality. All trained personnel assisting with the study will be instructed on the importance of protecting participants' confidentiality and will have successfully completed the required education on protection of human research participants. All paper and computer records will be identified only by subject number rather than by name. All study records will be stored in locked file cabinets and will only be available to the PI or other project staff. Computer data files (without subject identifiers) will be stored on computer servers with secure passwords and electronic storage devices will be encrypted. All study records will be stored in locked file cabinets and will only be available to the PI or other project staff. Study staff will be instructed to not record any information (e.g., responses to back pain criteria) obtained during the phone screen. Each intervention group will be audio-recorded (and video-recorded via Zoom) for the evaluation of therapist adherence to the protocol, and a random selection of 50% of all sessions conducted will be reviewed by the study PI and Co-I. No identifying information will be transcribed as the purpose of this digital recording is to assess treatment integrity. Once the audio recordings are reviewed and adherence is discussed with the study therapist, the recordings will be destroyed. Prior to destruction, the recordings will be kept in a locked filing cabinet in the laboratory of the PI. Video recordings via Zoom will only be used to extract an audio file, and video files will be promptly destroyed after each intervention visit.

8. Possible Discomforts and Risks: The risks for this study are minimal and appropriate safeguards are planned and in place to handle risks in a timely and appropriate manner.

Protection against potential risks:

Physical Performance Exam. The back performance test may cause participant discomfort as a result of the exam. The examiner will monitor the response of participants in order to gauge the need to discontinue the exam. Participants may stop at any time.

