Questionnaires. Participants will fill out several questionnaires about themselves. While these generally carry no associated risks, it is possible that participants might experience some feelings of discomfort or unease when reading or responding to survey questions that are personal. Throughout each questionnaire, participants will be reminded that participation is completely voluntary, and they can refuse to answer any question or can stop at any time. The PI, Co-I, and study interventionists are psychologists and are trained to deal with depression. Any participants whose responses during the group sessions or on the PROMIS Depression Short Form (raw score ≥ 33) indicate severe psychological distress (such as severe depression) will be interviewed by the site PI, Co-I, or other appropriately trained professionals for suicide risk and risk of harm to self and others. Participants will be assisted to the emergency room if danger is imminent or referred to either their physician or a mental health professional if necessary.

Intervention Integrity. To protect participants and maintain treatment integrity, the PI will thoroughly train research assistants/interventionists on the intervention protocol. The intervention will be manualized to augment treatment fidelity and the study PI will be available for consultation/supervision during intervention sessions and will hold weekly supervision meetings with interventionists to review the protocol and ensure treatment compliance. In addition, the Co-I ([name]) is a licensed clinical psychologist who will be available for consultation/supervision during the intervention sessions.

9. Possible Benefits: While persistent pain is common in older adults, chronic low back pain is the leading cause of disability in this population and results in significant impairments in psychosocial and physical functioning. Participation in this research will provide the participant with a first-hand look at pain research and provide them with the opportunity to participate in a new self-management treatment

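### The example attached to *unexpected* in the adverse-event text describes an expected event and so contradicts the term used in the 5-working-day reporting rule

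*Combined protocol and SAP*

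**What the plan says.** The text is in the combined protocol and SAP, section 7, Data and Safety Monitoring. No data and safety monitoring board is planned, and adverse events are recorded on a form developed by the university's IRB. The protocol describes that form as follows: "This form requires a description of the event, the course of action taken, and specification regarding whether or not the event was" one of three things. The first is "serious (e.g., life threatening, requiring or prolonging hospitalization, resulting in significant disability/incapacity or death"). The second is "unexpected (e.g., consistent with anticipated potential risks outlined in the study protocol/informed consent"). The third is a causal relation to the study interventions or procedures.

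The reporting rule comes next: "All serious and unexpected adverse events are to be reported to the University of Florida IRB (within 5 working days"), and to the sponsor as well. For the remainder: "Other types of adverse events will be monitored and reported to the University of Florida IRB in" the annual progress review. The section closes with a weekly check: "The investigators will review the reported adverse events on a weekly basis to minimize the risk to the study subjects".

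No other section defines *unexpected* or corrects the bracket.

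**The concern.** The bracket is meant to help staff decide whether an event is unexpected, yet it describes an event that was foreseen. The term is operative: together with seriousness, it separates reporting within 5 working days from the annual review. With no monitoring board, the reports to the IRB and sponsor are the only safety oversight outside the study team that the documents describe. An inverted example in that sentence could lead staff to send foreseen events down the fast route. On a stricter reading it could leave a serious unforeseen event on the slow one.

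**Working it through.** The plan states no figure on this point and no arithmetic applies. The check sets the wording of the list against the reporting rule that relies on it.

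**Step 1: the two brackets side by side.** Items 1 and 2 have the same form, a term followed by a bracket opening with *e.g.*

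| Item | What the bracket describes | Relation to the term |
|---|---|---|
| serious | life-threatening events, hospitalization, disability, death | instances of the term |
| unexpected | events in line with the risks already set out in the protocol or consent | instances of its opposite |

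The first bracket illustrates its own term. Nothing signals that the second works the other way round.

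**Step 2: the sense in which the rule uses the word.** The rule gives the fast route to serious and unexpected events and the annual review to the rest. That is coherent if *unexpected* has its ordinary meaning, so the fault lies in the bracket and not in the rule.

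**Step 3: a concrete application.** Section 8 says the back performance test may cause discomfort. Of the questionnaires it says that "participants might experience some feelings of discomfort or unease when reading or responding to survey questions that are personal". Both are anticipated risks. Taken at its word, the bracket would give them as examples of unexpected events.

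**Step 4: what each reading does to reporting.** *Foreseen* here means consistent with the outlined risks, and *unforeseen* means not consistent with them. The rule does not say whether an event must be both serious and unexpected or only one of these, so both are shown.

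| Reading of the bracket | Events classed as unexpected | Change in route if both conditions are required | Change in route if either suffices |
|---|---|---|---|
| Ordinary meaning, bracket ignored | unforeseen | none (reference) | none (reference) |
| Bracket adds examples to the ordinary meaning | unforeseen and foreseen | serious foreseen events move from annual review to 5 working days | non-serious foreseen events move from annual review to 5 working days |
| Bracket taken as the definition | foreseen only | serious foreseen events move to 5 working days; serious unforeseen events move to annual review | non-serious foreseen events move to 5 working days; non-serious unforeseen events move to annual review |

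Read as an added example, the bracket causes over-reporting only and delays nothing. A serious event is delayed only if the bracket is taken as an exclusive definition, both conditions are required, and the event lies outside the outlined risks.

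**The case against.** The strongest defence is that the sentence will mislead nobody.

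- **It is an example, not a definition.** The bracket opens with *e.g.*, and elsewhere the protocol writes *i.e.* when it defines something, for example when it names the resilience targets or explains screen failures. An example does not remove unforeseen events from a word that plainly covers them. This stands, and it is why delay cannot be presented as the natural result of the text.
- **It may name the test rather than an instance.** Since the form asks whether or not an event was unexpected, the bracket could point to the comparison to make, or illustrate a *no* answer. This is weak. The parallel item illustrates its own term, and a bare test would not tell staff which answer makes an event unexpected.
- **The context corrects it.** Staff complete the IRB's form, not the protocol's paraphrase of it. The form's title refers to unanticipated problems, and the form may carry a sound definition. Personnel are trained in the protection of research participants, interventionists have weekly supervision meetings, and the investigators review events weekly. This stands as a reason to think misrouting unlikely. It does not cure the wording: the form is not shown, and none of these steps is stated to trigger a report to the IRB.

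A reader might go further and infer that serious events in this trial would be held back. Section 8 might seem to supply a case: it provides for severe distress and suicide-risk interviews, while discomfort or unease is the only questionnaire effect it names as possible. The documents do not support that inference. The severe-distress text itself sits under the heading on protection against potential risks, so such an event may well count as an outlined risk. The bracket also refers to the informed consent, which is not in the text available here. Whether severe distress is a listed risk therefore cannot be settled.

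**Conclusion.** The contradiction is certain on the face of the text: the example given for *unexpected* describes an expected event, and nothing in the documents corrects it. That a *not* was dropped is the likely explanation, not an established fact.

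The practical consequence is small and conditional. If staff followed the example, foreseen events could be over-reported. Delay of a serious unforeseen event needs the further conditions shown in the working, and the documents establish none of them. No frequency of misrouting and no length of delay can be put on this: the documents give no adverse-event rate and state that "The risks for this study are minimal". Feasibility, acceptability and outcome results are unaffected. This is a minor correction to safety-reporting text.

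**What to change.** Insert *not* before *consistent* in the bracket after *unexpected*, so that the example covers events that do not fit the risks outlined in the protocol or consent. Then check the sentence against the definition on the IRB's form, so that the two agree.

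The cost is one word and one comparison, submitted as a minor protocol revision. Data collection and analysis do not change.

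A separate and optional edit would state whether the 5-working-day rule requires an event to be both serious and unexpected, or either. The bracket needs correcting whichever is meant.
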